Document date: 07/18/2023

Impacts of mitochondrial-targeted antioxidant on leg function, leg blood flow and skeletal muscle mitochondrial function in peripheral artery disease patients: full study protocol and statistical analysis plan

NCT# 03506633

Study protocol

Participants

Patients with PAD (n = 13, 7 males and 6 females) were recruited for study participation. Disease staging, claudication history, and ankle-brachial index of <0.90 were determined by both self-report and by physician diagnosis, and all participants were classified as Fontaine stage IIa and IIb (16). Participants were also required to have a stable BP, lipid, and/or diabetes regimen for \geq 6 wk prior to participation, and all females were postmenopausal (no menses for \geq 12 consecutive months). Participants were excluded from the study if they had a history of pain at rest (Fontaine stage III) and/or tissue loss due to PAD (Fontaine stage IV), limited walking capacity due to conditions other than PAD, or renal disease. Participants were also asked to track what they consumed the day before their first visit so they could consume the same foods prior to their second visit. In addition, participants were requested to not alter their digtary habits during the 2 wk washout period. All procedures were performed according with the protocols approved by the Institutional Review Board and performed in accordance with the Declaration of Helsinki. All participants provided written, informed consent prior to beginning the study. This study was registered with https://clinicaltrials.gov/ (NCT03506633).

Design

This study used a randomized, double-blinded, placebo-controlled, crossover design with a washout period of 14 days between the 2 study visits (**Fig. 1**). Participants were randomly assigned to receive either 80 mg of MitoQ or placebo. In a previous study, MitoQ showed pharmacokinetic behavior at doses of 80 mg (1mg/1kg), resulting in plasma maximal concentration of 33.15 ng.ml, which is safe for humans. Additionally, administration of 20 mg/1kg of mitoQ was shown to have no toxicity in previous research. The dose in this study was considerably lower than this amount. These findings led us to believe the recommended

80 mg dose is ideal for this study. The PL consisted of tapioca powder capsules that possessed no nitrate or antioxidant properties. Participants were informed that we were researching the effects of commercially available juice and pills on their vascular function and walking capacity; therefore, they were not aware that the capsules were PL. All assessments were performed after an overnight fast and at the same time of day (9:00 AM \pm 1 h). Anthropometric measurements were obtained upon arrival at both visits. Following anthropometrics, baseline experimental measurements were conducted, after which the MitoQ supplement or PL were consumed. All experimental measurements were repeated ~ 1 h following ingestion. All data analyses were performed in a blinded manner.

Anthropometrics

Anthropometric measurements included height, body mass, and body composition. Height was measured using a stadiometer (nearest 0.5 cm). Body mass was measured using a standard scale (nearest 0.1 kg), and body mass index was calculated by taking the body mass divided by height squared (kg/m²). Body fat percentage was assessed using bioelectrical impedance analysis in duplicate to the nearest 0.1% (HBF – 306C, Omron Healthcare, Lake Forest, IL), and the average of the 2 measures was recorded as the body fat percentage.

Resting heart rate and blood pressure

Participants sat for 15 min in a quiet and temperature-controlled room. Resting heart rate and BP were assessed in duplicate using an automated sphygmomanometer (HEM – FL 31, Omron Healthcare, Lake Forest, IL). The two measurements were taken with 5 min separating each measurement, and the average of the 2 was recorded as the resting heart rate and BP.

Endothelial function

Endothelial function was assessed using brachial artery flow-mediated dilation (FMD) and popliteal artery FMD using a Doppler ultrasound (Terason uSmart 3300, Terason Division Teratech Corporation, Burlington, MA), rapid inflation cuff system (E20 Rapid Cuff and cuff model SC5, D.E. Hokanson, Bellevue, WA), and a 3-lead electrocardiogram system (7700 Series

Trigger Monitor, IvyBiomedical Systems Inc., Branford, CT) as previously described (22). Briefly, for both brachial and popliteal assessments, the rapid inflation cuff was placed just distal to the antecubital fossa and just distal to the popliteal fossa, respectively (22). For both assessments, resting arterial diameter was recorded with the ultrasound probe ~ 1-2 cm proximal to the rapid-inflation cuff for 5 min (22). The cuff was inflated to a pressure of 250 mmHg after baseline diameter was obtained and remained inflated for 5 min (22). The cuff was then deflated and the reactive hyperemic arterial response was recorded continuously on R-wave trigger for 5 min (22). Data were analyzed using an image capturing and automated edge-detection software (Vascular Imager, Vascular Research Tools 6, Medical Imaging Applications, Coralville, IA) as previously described (22).

Walking capacity and skeletal muscle oxygen utilization capacity

Maximal walking capacity was assessed on a standard treadmill (Lode, B.V, Groningen, The Netherlands) using the modified Gardner protocol (22, 24). Participants were asked to notify the test administrators about their onset of claudication (the exact moment their leg pain starts) and to walk as long as they could tolerate even if the claudication persisted (maximal walking time and distance). The test was ended once patients could not tolerate their symptoms (i.e., severe claudication).

Gastrocnemius oxygen utilization capacity was measured with a portable near-infrared spectroscopy (NIRS) unit (Artinis PortaMon, Einsteinweg, The Netherlands) and Oxysoft software (v. 3.0.103.3, Einsteinweg, The Netherlands) during the exercise testing as previously described (22). Briefly, the NIRS device was adhered to the gastrocnemius, at the approximate location where the participant felt the most pain, using a commercially available double-sided adhesive and a commercially available black bandage to prevent extraneous light from reaching the device (15, 22). NIRS data were collected continuously at a frequency of 10 Hz and used to

estimate the change in tissue saturation (StO₂), deoxygenated hemoglobin concentration ([HHb]) and oxygenated hemoglobin concentration ([O₂Hb]) at resting baseline and during the walking test. Upon walking test completion, the participant stood in a resting standing position and a thigh rapid inflation cuff (cuff model SC10, D.E. Hokanson, Bellevue, WA) was placed on the thigh ~ 3-4 centimeters proximal to the knee on the limb with the NIRS device. The cuff was inflated to ~ 250- 260 mmHg for 5 min to deoxygenate the tissue with the same rapid inflation cuff system used for FMD (22, 25). The cuff pressure was released after 5 min, and the peak hyperemic response following cuff release was used to determine the 100% oxygenation level for each participant and was used to calculate normalized [HHb] (22, 25). The raw NIRS data were reduced to 1 Hz files and exported to Microsoft Excel files for later analysis.

Autonomic function

Autonomic nervous system function was measured using heart rate variability. Participants wore a simple heart rate monitor (Suunto Smart Sensor, Suunto, Vantaa, Finland). The researcher assisted the participant with putting on the heart rate monitor. The participant was positioned in a supine position on a padded examination table for 5 minutes. The subject was then be assisted with standing upright in front of the table for 5 minutes. Heart rate was recorded during supine and standing positions and used to determine autonomic nervous activity.

Statistical analysis

The Shapiro-Wilk test was used for all dependent variables to determine the normality of the data. Independent *t*-tests were used to determine any differences between subject characteristics at the MitoQ and PL visits. A two-way repeated measures analysis of variance³ (ANOVA) [group (MitoQ and PL) x time (before and after supplement intake)] was used to compare the changes between MitoQ and PL intake within and between groups on the dependent variables. When a significant main effect or interaction was found, paired *t*-tests were used for *post-hoc* comparisons for the normally distributed variables, and paired samples

3

Wilcoxon tests were used for non-normally distributed variables. Based on a power calculation from a previous study, a sample size of a minimum of total 14 (n = 7 per group) would allow for 80% power to detect differences between FMD between MitoQ vs. PL (26). Associations between dependent variables were assessed using Pearson's product-moment correlation coefficient. Effect size analyses were conducted using Cohen's *d* and interpreted as 0.2 as a small effect size, 0.5 as a medium effect size, and 0.8 as a large effect size (22, 27). All analyses were performed using SPSS 26.0 (IBM, Armonk, NY). Descriptive characteristics are presented as Mean \pm SD, and all other data are presented as Mean \pm SE. Statistical significance was set to *p* < 0.05.

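### The normality check that chooses between the paired t-test and the Wilcoxon test appears to be made on the variables themselves, although both tests depend on within-person differences: a minor error with a small effect

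*Combined protocol and SAP*

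**What the plan says.** All of the text on this point is in the Statistical analysis section.

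- Normality: "The Shapiro-Wilk test was used for all dependent variables to determine the normality of the data".
- Main model: a two-way repeated measures ANOVA, "group (MitoQ and PL) x time (before and after supplement intake)] was used to compare the changes". It is run whatever the normality result, and no non-parametric alternative is given.
- Gate: post-hoc tests follow only "When a significant main effect or interaction was found".
- Choice of post-hoc test: "paired *t*-tests were used for *post-hoc* comparisons for the normally distributed variables", while paired-sample "Wilcoxon tests were used for non-normally distributed variables".

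The Participants section gives the number of patients: "Patients with PAD (n = 13, 7 males and 6 females) were recruited for study participation". The Design section describes a "crossover design with a washout period of 14 days between the 2 study visits", so every patient contributes paired data.

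Nothing in the document names differences, change scores or residuals as the object of the Shapiro-Wilk test.

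**The concern.** In a crossover with paired tests, a patient's own level cancels out. The paired t-test needs approximately normal differences, and the signed-rank test needs approximately symmetric ones. How an outcome is spread across 13 patients says little about either. A check on the outcome's own values can therefore err in two directions:

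- Patients differ in a skewed way but their changes are normal. The variable is sent to Wilcoxon without need.
- Patients look normal but a few have outlying changes. The variable is sent to the t-test, which has less power there.

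The post-hoc tests give the pre-post and MitoQ-placebo p-values for each outcome. With so few patients, a borderline result could change with the choice of test.

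**Working it through.** The plan gives no figure on this point to reproduce.

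**Inputs.** From the documents: n = 13, crossover, alpha 0.05 (two-sided assumed). Not in the documents, so assumed: all distributions and the within-person correlation ρ.

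**Step 1: why the quantity matters.** Write an outcome as Y = b + e, with b the patient's level and e the within-patient part. Then ρ = var(b) / [var(b) + var(e)]. The difference between two occasions is e2 − e1 plus any effect, and b drops out. At ρ = 0.8 to 0.9, 80 to 90% of the variance of Y comes from b and plays no part in either paired test.

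**Step 2: the two rules compared, without the ANOVA gate.** Each scenario had 5,000 runs of 13 pairs, with Shapiro-Wilk at 5%. Ranges cover two versions of the raw-value rule: either condition flagged, or both conditions pooled. The raw check was made before the effect was added. Except in the lognormal row, the effect was 0.85 SD of the difference, which gives a paired t-test 80% power with 13 normal pairs.

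| Assumed scenario | Raw check flags | Difference check flags | Rules disagree | Type I error, raw / difference | Power, raw / difference |
|---|---|---|---|---|---|
| All normal, ρ 0.7 | 7.7–9.8% | 5.0% | 11.7–13.9% | 4.9–5.0 / 5.0% | 80.2–80.4 / 80.4% |
| Skewed patients (log-SD 0.8), normal within, ρ 0.7 | 30.7–32.2% | 4.5% | 32.8–34.4% | 4.9 / 5.0% | 79.5–79.6 / 80.4% |
| Same, ρ 0.9 | 51.7–56.6% | 4.3% | 51.5–56.0% | 5.2 / 5.4% | 79.1–79.2 / 80.2% |
| Normal patients, t (3 df) within, ρ 0.7 | 12.6–14.5% | 18.4% | 21.7–22.0% | 4.3–4.4 / 4.9% | 86.9–87.2 / 88.5% |
| Normal patients, exponential differences | 13.3–16.2% | 48.6% | 42.0–43.9% | 8.7 / 10.3% | 94.9–95.0 / 96.0% |
| Multiplicative lognormal (log-SD 0.7 between, 0.25 within; shift 0.3) | 70.4–82.8% | 35.5% | 44.6–51.1% | 4.3–4.4 / 4.4% | 60.8–61.2 / 59.8% |

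The rules often disagree, but 12 to 14% disagreement arises even when everything is normal. The largest power gain from checking differences is 88.5 − 86.9 = 1.6 points. In the lognormal row the raw rule is ahead, by at most 61.2 − 59.8 = 1.4 points. Where differences are symmetric, type I error moves by at most 4.9 − 4.3 = 0.6 points.

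**Step 3: outlying changes, without the gate.** Here the shift is 0.8 SD of the uncontaminated difference.

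- 15% of patients with 5 times the SD in their differences, ρ 0.9: power 44% (raw) against 50% (difference), a gap of 6 points. The least favourable version of the raw rule gave 42%, a gap of 8.
- Differences following t with 2 df, ρ 0.9: 60% against 65%, a gap of 5 points.
- Outliers arising in every measurement instead of in the differences: gaps of about 1 to 2.5 points (for example 39% against 40% at ρ 0.8).

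**Step 4: with the gate the plan imposes.** Success means that at least one ANOVA effect is significant and the MitoQ pre-post test is significant. Raw against difference rule:

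- 5-times-SD outliers: 27% against 28%.
- t with 2 df: 20–22% against 21–22%.
- Skewed patients: 68–70% against 69–71%.

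The largest gap here was 1.3 points, and across gated runs it was 0 to 2 points. The significance call changed in about 1 to 5% of simulated trials with a true effect. This range is not a bound. Placing the outliers directly in the change scores can give a gated gain above 2 points, though below the ungated gain for the same data.

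**The case against.** **The document never says raw.** It does not mention separate cells, pooling, change scores or residuals. A reader might infer that the raw values were certainly tested. The text does not establish that. It is the natural reading, because normality is attributed to the dependent variables and the test is then chosen per variable. If differences were in fact tested, the sentence still needs correcting, because it does not say so.

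**A reader might infer that the rule often picks a wrong or invalid test.** This is not supported. With normal differences Wilcoxon is valid and costs about 2 points of power (about 78% against 80%). High flag rates for skewed patients, 42 to 66% against 4 to 5% for differences, count a variable as non-normal if any of four cells is flagged. The plan states no such rule, and it flags about 15% of trials when everything is normal.

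**A reader might infer a 5 to 6 point power loss.** Those figures leave out the ANOVA gate and come from strongly contaminated differences at ρ 0.9.

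**The remedy is itself imperfect.** Shapiro-Wilk on 13 differences flagged only 18% of the t (3 df) samples and 49% of the exponential ones. In one set of outlier runs, always using Wilcoxon (42–43%) did slightly better than choosing by the differences (40–41%). With skewed differences the difference rule had the higher type I error for the mean (10.3% against 8.7%), because the signed-rank test assumes symmetry.

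These objections stand as limits on the size of the problem. None of them shows that a variable's own distribution is the right thing to check before a paired test.

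**Conclusion.** The point holds as a minor error of specification. As worded, the check is apparently keyed to the variables' own values, while the tests it selects depend on within-person differences. It can therefore switch tests for no valid reason.

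With n = 13 and an assumed intraclass correlation of 0.8 to 0.9, the cost is about 0 to 2 points of power after the ANOVA gate. Without the gate it is up to about 4 to 6 points in most constructions, and 8 in the most extreme one. There is no meaningful change in type I error when differences are symmetric. Skewed differences are not repaired by either rule. Every figure depends on distributions and correlations that the documents do not give.

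A reader might go further and send the interaction to a t-test or Wilcoxon choice as well. The documents do not support that: the plan tests the interaction in the ANOVA, and the normality rule governs only the post-hoc comparisons.

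**What to change.** Replace the normality sentence with wording to this effect: normality is assessed by Shapiro-Wilk and a Q-Q plot on the within-person difference for each paired post-hoc comparison, and on the residuals for the repeated measures ANOVA; the paired t-test or Wilcoxon signed-rank test is chosen for each post-hoc comparison from its own differences; the interaction is tested in the ANOVA.

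Then re-run the normality checks and any post-hoc test whose choice changes. Where a choice changes, report both results so that the reader can see whether the conclusion depends on it.

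The cost is one or two sentences and a short re-analysis. The document reports recruitment and analysis in the past tense, so the data appear to be held already and no new data are needed. One consequence to accept openly is that different comparisons of the same outcome may use different tests.

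### Independent t-tests are named for characteristics measured on the same 13 people at both crossover visits; the data are paired, and if the visits are positively correlated the p-values are too large

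*Combined protocol and SAP*

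**What the plan says.** On subject characteristics, the Statistical analysis section states: "Independent *t*-tests were used to determine any differences between subject characteristics at the MitoQ and PL visits".

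The Design section describes the trial thus: "This study used a randomized, double-blinded, placebo-controlled, crossover design with a washout period of 14 days between the 2 study visits". The Participants section gives the number: "Patients with PAD (n = 13, 7 males and 6 females) were recruited for study participation". It also asks participants to "track what they consumed the day before their first visit so they could consume the same foods prior to their second visit", so each person has two visits. Design adds: "Anthropometric measurements were obtained upon arrival at both visits".

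For the outcomes, the Statistical analysis section names a repeated measures ANOVA of group by time. On the follow-up tests it says that "paired *t*-tests were used for *post-hoc* comparisons for the normally distributed variables", and names the paired-samples form of the Wilcoxon test for variables that are not normally distributed.

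The documents do not list which variables count as subject characteristics.

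**The concern.** An independent t-test assumes that the two samples are unrelated. Here they are one group of 13 people measured twice, once at the MitoQ visit and once at the placebo visit. The test ignores the covariance between a person's two values. When that covariance is positive, the standard error is too large and so is the p-value.

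The section is also inconsistent. It treats the two visits as paired for the outcomes and as unpaired for the characteristics, and gives no reason.

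At stake is the use of the comparison as reassurance. Its purpose is to show that patients were alike at the two treatment visits. A test that seldom rejects will usually report no significant difference, whether or not one exists.

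**Working it through.** **Inputs.** n = 13 (Participants); the same people at both visits (Design); significance level 0.05 (Statistical analysis), taken as two-sided because the plan does not say. The between-visit correlation r is not given, so it is assumed over 0.3 to 0.9. SDs are taken as equal at the two visits. The plan states no figure of its own on this point to reproduce; its sample-size figure concerns FMD and has no bearing here.

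**Step 1: standard error of the mean difference.**

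- Independent test: SD × sqrt(2/n).
- Correct for paired data: SD × sqrt(2(1-r)/n).
- Ratio: 1/sqrt(1-r). At r = 0.5 this is 1/sqrt(0.5) = 1.41; at r = 0.9 it is 1/sqrt(0.1) = 3.16.

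**Step 2: type I error and power.** Bivariate-normal trials of 13 pairs were simulated. The independent test has 24 df and critical t 2.064; the paired test has 12 df and critical t 2.179. For power, the true MitoQ-versus-placebo difference was set where the paired test has 80% power. That is 0.847 SDs of the within-person difference (dz = 0.847, noncentral t), or 0.847 × sqrt(2(1-r)) in units of the between-person SD.

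| Assumed r | SE too large by | Type I error, independent test | Power, independent test (paired test 80%) |
|---|---|---|---|
| 0.3 | 1.20 | 2.2% | 72% |
| 0.5 | 1.41 | about 0.85% | 56% |
| 0.7 | 1.83 | 0.15% | 29% |
| 0.8 | 2.24 | 0.03% | 13% |
| 0.9 | 3.16 | about 0.001% | 1.5% |

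The paired test stays at about 5% type I error throughout. At r = 0 nothing is lost: the independent test holds 5% and has 83% power.

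**Step 3: 95% CI half-width for the mean difference, in SD units.**

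- Independent: 2.064 × sqrt(2/13) = 0.81.
- Paired, r = 0.5: 2.179 × sqrt(1.0/13) = 0.60.
- Paired, r = 0.8: 2.179 × sqrt(0.4/13) = 0.38.
- Paired, r = 0.9: 2.179 × sqrt(0.2/13) = 0.27.

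**Step 4: what a paired test would not do.** A change between visit 1 and visit 2 is a period effect. In a MitoQ-versus-placebo comparison its sign reverses between the two treatment orders, so it largely cancels. For a period shift of dz = 0.847, a paired MitoQ-versus-placebo test rejects 1.3%, 3%, 8% and 18% of the time at assumed order splits of 7/6, 8/5, 9/4 and 10/3. A paired visit-2-versus-visit-1 test rejects 80% of the time. The documents do not give the order split.

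**The case against.** The strongest objection is that the error has almost no consequence. The test feeds no treatment estimate, and the outcomes are analysed by repeated measures ANOVA with paired follow-up. Pre-intake values of the outcomes are measured at each visit and enter that ANOVA. Random assignment, stable medication regimens, repeated diet, fasting and a fixed time of day all work towards comparable visits. This stands, and it sets the severity.

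Second, under randomisation a systematic MitoQ-versus-placebo difference before intake is not expected, apart from chance or carryover. The more realistic worry is a shift over the washout, which Step 4 shows a paired treatment comparison would rarely detect. This also stands. Changing the test corrects the reported p-values but adds little protection, and describing both visits without a test is a reasonable alternative.

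Third, the test is conservative only if r is positive. At r = -0.3 its type I error is 8.4%. The condition is needed, but positive correlation is to be expected for body mass, BMI and body fat in the same person about two weeks apart.

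Fourth, the affected variables are not specified. If resting heart rate and blood pressure count as outcomes, the paired methods already cover them and only a few anthropometric items remain. That narrows the point but does not remove it.

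Finally, an independent test would suit a comparison of the two randomised order groups. The sentence names visits, however, so it would need correcting under that reading too.

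**Conclusion.** The concern holds, as a minor one. The pairing follows from the crossover design, and nothing elsewhere in the document repairs the sentence. That conclusion needs no assumption about r.

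The size does depend on r. Under positive correlation, equal SDs and normality, the figures in the table apply, and the loss is already material at r = 0.5: a true difference that a paired test would find 80% of the time is found 56% of the time. A non-significant result from the named test should not be read as showing that the visits were alike. The treatment-effect analysis is unaffected.

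**What to change.** In the Statistical analysis section, replace the independent t-tests with paired t-tests for characteristics measured at both visits, or with Wilcoxon signed-rank tests where the within-person differences are not normal. Report the mean within-person difference with its 95% CI. List the characteristics compared, and present once-only items such as age and sex descriptively with no test. Describing the values at both visits without any test would also remove the error.

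If stability over the washout is to be shown, add a separate paired comparison of visit 2 with visit 1. If the order groups were what was meant, say so.

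The cost is one sentence and re-running a few tests on data already collected.

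### The two-visit crossover of 13 people is analysed without a period term and without the pre-dose value as a covariate, which can cost precision and, if the sequence split is uneven, bias the estimate

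*Combined protocol and SAP*

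**What the plan says.** The Design section describes a randomised, placebo-controlled "crossover design with a washout period of 14 days between the 2 study visits". At each visit "baseline experimental measurements were conducted, after which the MitoQ supplement or PL were consumed", and then "All experimental measurements were repeated ~ 1 h following ingestion". Each participant therefore supplies four values per outcome: pre-dose and post-dose, on MitoQ and on placebo. The Participants section gives the number: "Patients with PAD (n = 13, 7 males and 6 females) were recruited for study participation".

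The Statistical analysis section specifies a two-way repeated measures ANOVA: "group (MitoQ and PL) x time (before and after supplement intake)] was used to compare the changes between MitoQ and PL intake". Follow-up tests are triggered as follows: "When a significant main effect or interaction was found". They are paired t-tests, while "Wilcoxon tests were used for non-normally distributed variables". The pairs to be compared are not named. No period, visit-order or sequence term appears, and no pre-dose covariate. The randomisation method and the number of participants per sequence are not stated; Fig. 1 is not available in the text reviewed. The power statement reads "a sample size of a minimum of total 14 (n = 7 per group) would allow for 80% power to detect differences between FMD", and does not say whether group there means sequence.

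**The concern.** In a randomised crossover, visit is a known source of variation, and order is randomised so that it can be separated from treatment. A model with only treatment and time does not separate them. What follows depends on the kind of visit effect.

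- **A constant shift between visits**, moving pre-dose and post-dose values equally, cancels from the interaction. It does not cancel from the group main effect, which the plan also acts on, nor from any post-hoc comparison of raw MitoQ and placebo values. A before-versus-after comparison within one treatment would be free of it.
- **A visit effect on the within-visit change** does not cancel from the interaction. It is conceivable for a treadmill test walked to the limit of tolerance and repeated about an hour later, though nothing in the documents shows it. They give no mechanism for FMD, the only outcome with a power statement.

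Separately, subtracting the pre-dose value is less efficient than using it as a covariate unless pre-dose and post-dose differences are highly correlated. Any Wilcoxon test comparing MitoQ with placebo has the same gaps. With 13 participants against a stated minimum of 14 there is little precision to spare, and the main risk is missing a real effect.

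**Working it through.** **Inputs from the documents.** N = 13; two visits in randomised order; pre-dose and post-dose values at each; model factors treatment and time; significance level 0.05 (two-sided assumed).

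**Assumptions.** Normal errors; sequence split n1/n2; period effect π on the change, in SDs of D (defined in step 1); and ρ, the correlation between pre-dose and post-dose MitoQ-placebo differences.

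**The plan's own figure.** The minimum of 14 cannot be reproduced, because no difference, SD or correlation is given. By the t distribution it implies an effect of 0.81 SD for 14 paired participants, or 1.63 SD for two independent groups of 7. With 0.81 SD paired, 13 participants give 76.5% power. To isolate the model choice, the effect below is set to δ = 0.847 SD, which gives the planned test exactly 80% at N = 13 with no period effect.

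**Step 1: what is tested.** With both factors within participant, the interaction is a one-sample t-test (12 df) on D = (post − pre on MitoQ) − (post − pre on placebo).

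**Step 2: bias.** D = δ + π + e in one sequence and δ − π + e in the other, so the mean of D is off by π(n1 − n2)/13:
- 7/6: 1/13 × 0.5 = 0.04 SD
- 8/5: 3/13 × 0.5 = 0.12 SD
- 9/4: 5/13 × 0.5 = 0.19 SD, and 5/13 × 0.8 = 0.31 SD

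**Step 3: interval width at 7/6, π = 0.5.** Without a period term the variance of D becomes 1 + π² × 4n1n2/(13 × 12) = 1 + 0.25 × 168/156 = 1.269. The half-width is 2.179 × √1.269/√13 = 0.681. With the term (11 df) it is 2.201 × ½√(1/7 + 1/6) = 0.612. The ratio is 1.11. In simulation the planned interval is 1%, 11% and 29% wider at π = 0.2, 0.5 and 0.8.

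**Step 4: simulated power and type I error** (200,000 runs per cell; two planned figures are the two directions of the period effect).

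| Split | π (SD) | Power, planned | Power, period term | Type I error, planned |
|---|---|---|---|---|
| 7/6 | 0.2 | 77% or 80% | 79% | 4.6% |
| 7/6 | 0.5 | 68% or 76% | 79% | 3.1% |
| 7/6 | 0.8 | 52% or 67% | 79% | 1.5% |
| 9/4 | 0.5 | 50% or 89% | 73% | 6.7% |
| 9/4 | 0.8 | 25% or 90% | 73% | 7.8% |

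At 8/5 and π = 0.5, planned power is 59% or 83% against 77%.

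**Step 5: averaged over simple randomisation.** The chances are 42% for 7/6, 31% for 8/5 and 27% for 9/4 or worse. Average bias is zero and planned type I error is 5.0–5.1% throughout. Power, planned against period term alone, is 80% v 76% (π = 0), 79% v 76% (0.2), 71% v 76% (0.5) and 59% v 76% (0.8).

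**Step 6: adding the covariate.** In units of the SD of the between-visit difference, the change score has variance 2(1 − ρ) and the covariate-adjusted estimate 1 − ρ², so their ratio is 2/(1 + ρ): 2.00 at ρ = 0, 1.33 at 0.5 and 1.11 at 0.8, before the cost of lost degrees of freedom. With period and covariate together (10 df), averaged over simple randomisation, power at ρ = 0, 0.3, 0.5, 0.7, 0.8 and 0.9 is 94, 87, 82, 78, 75 and 73%. The planned test has 80% with no period effect and 71% at π = 0.5.

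**Step 7: group main effect.** Under a constant visit shift of 0.8 SD of its own difference, its type I error is 1.5% at 7/6 and 8% at 9/4 (bias 0.06 and 0.31 SD), while the interaction stays at 5%.

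**The case against.** Four points deserve weight.

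- **The harm is conditional.** Bias of any size needs a visit effect on the change of roughly 0.5 SD or more and a split well away from 7/6, and neither is documented. At 7/6 the test is conservative. The design also limits visit effects: repeated food intake on the preceding day, unchanged diet during washout, stable medication, overnight fasting, a fixed time of day, and a fresh pre-dose measurement at each visit. This stands as a limit on size. The controls do not exclude learning or fatigue on a repeated treadmill test.
- **The remedy can lose power.** With no period effect, the period term alone takes power from 80% to 76% averaged over simple randomisation, and the full model falls below the planned test once ρ exceeds about 0.6. This stands; ρ is not in the documents. The change-score comparison is a valid estimate, so the covariate is a matter of efficiency.
- **The planned test is inferred.** The plan also refers to comparisons between groups and uses independent t-tests for characteristics at the two visits. If treatment was entered as a between-participant factor, the figures above describe a different test. The repeated measures label supports the paired reading, but the point is not certain.
- **The main effect may be only a gate.** The stated aim is to compare changes, so a significant main effect may do no more than open the post-hoc tests. Whether a period shift reaches a reported result then depends on pairs the plan does not name.

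**Conclusion.** The concern holds. The plan uses neither the randomised order nor the pre-dose value as a covariate, and nothing else in the documents makes good the omission. The issue is precision, and bias conditional on the split, rather than an overall excess of false positives. At 7/6 the bias is only 1/13 of the period effect: negligible loss at 0.2 SD, but 4 to 12 power points at 0.5 SD (80% to 76% or 68%). At 9/4 with 0.5 SD, bias is 0.19 SD and type I error 6.7% for that split.

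These sizes rest on assumed period effects, correlations, splits and normal errors, and on the paired reading of the ANOVA. Confidence in the magnitude is therefore medium. The change is recommended because it is cheap and uses data already collected; it is not a fatal flaw.

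**What to change.** Pre-specify the following or, if the ANOVA is already reported, add it alongside as a labelled sensitivity analysis.

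1. For each outcome, regress each participant's post-dose MitoQ-placebo difference on the pre-dose MitoQ-placebo difference (uncentred, so that zero means no pre-dose difference) and a sequence indicator coded +1/−1. Report the intercept with its 95% confidence interval (10 df) as the treatment effect. Do not take the treatment effect from the group main effect.
2. Add period and covariate together, and fix the model in advance, not according to the observed ρ.
3. For non-normal outcomes, write the same model on visit 1 minus visit 2 differences and obtain the p-value by permuting sequence labels among participants (1,716 allocations at 7/6; within blocks if blocks were used). A simpler option is an exact rank-sum comparison, between sequences, of the visit 1 minus visit 2 difference in change; half its Hodges-Lehmann shift is the effect.
4. Report the number randomised to each sequence, and name the post-hoc pairs.

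**Cost.** SAP wording, one re-analysis and two degrees of freedom (12 to 10). With no period effect, the period term alone costs about 1 power point at 7/6, 3 at 8/5 and 7 at 9/4. The full model breaks even with the planned test near ρ = 0.7 at 7/6 and near 0.5 at 9/4, and costs power above those values. With assumed t errors on 3 df at 7/6 and no period effect, label permutation has 89% power at ρ = 0.5 and 85–86% at 0.8, against 88–89% for a signed-rank test on change differences. The rank-sum option has 81–82%, partly because its exact size at 7/6 is only 3.5%. None of this tests carry-over, which still rests on the 14-day washout.
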